3.0 Patient Eligibility

3.1 Inclusion criteria

1. Eligible patients will be aged \geq 18 years. Pediatric patients age 2 years and older will be considered on a case by case basis.
2. Diagnosis of Blastic Plasmacytoid Dendritic Cell Neoplasm (BPDCN) according to WHO classification or confirmed by hematopathology.^{24,25}
3. The patients must be in partial response or better (see Appendix A.).
4. $>$ 30 days post-transplant without active or chronic infections.
5. Karnofsky performance status \geq 60%; Lansky \geq 60 (see Appendices B. and C.).

6. LVEF \geq institutional lower limit of normal by MUGA scan or echocardiogram within 30 days of first protocol treatment.
7. Pulmonary function: DLCO, FEV1, FVC $> 40\%$ of predicted value (corrected for hemoglobin) within 3 months of registration.
8. Adequate organ function:
 - a. Serum creatinine ≤ 1.5 mg/dL (133 mmol/L).
 - b. Serum albumin ≥ 3.2 g/dL (or ≥ 32 g/L) without IV albumin within the previous 72 hours.
 - c. Bilirubin $\leq 1.5 \times$ the upper limit of normal ([ULN] except patients with Gilbert syndrome in whom bilirubin level of $> 1.5 \times$ ULN will be allowed).
 - d. AST and ALT ≤ 2.5 times ULN.
 - e. Hemoglobin ≥ 8 g/dL with or without transfusion in the last 7 days.
 - f. Absolute neutrophil count (ANC) ≥ 1000 without GCSF or GM-CSF in the last 2 weeks prior to screening.
 - g. Platelets $\geq 50,000$ /mL.
9. For allo-HCT, no \geq grade 2 visceral (gut or liver) acute GVHD and no \geq grade 3 or any other acute GVHD (Patients with chronic GVHD will be allowed at the discretion of the investigator).
10. Patient agrees to use acceptable contraceptive methods for the duration of time in the study, and to continue to use acceptable contraceptive methods for 2 months after the last tagraxofusp infusion.
11. Woman of child bearing potential (WOCBP) with a negative serum or urine pregnancy test within 14 days of tagraxofusp treatment.
12. Patient or patient's legal representative, parent(s) or guardian able to sign informed consent.
13. The patient can adhere to the study visit schedule and other protocol requirements, including follow-up for survival assessment.

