4.4 Dose and schedule

First three patients:

- Cycles 1-4: Tagraxofusp 9 mcg/kg IV on Days 1, 2, and 3.
- Cycles 5 and beyond: Tagraxofusp 12 mcg/kg IV on Days 1 and 2 (if no unacceptable toxicities at the 9 ug/kg/day IV dose, as defined in the statistical section).

Patient number 4 and beyond:

- Cycles 1-4: Tagraxofusp 12 ug/kg/day IV on Days 1, 2, and 3.
- Cycles 5 and beyond: Tagraxofusp 12 ug/kg/day IV on Days 1 and 2.

Cycle Length: 28 days

During a 28-day cycle, if the patient experiences related non-hematological toxicity with resolution to Grade ≤ 1 or baseline by day 28, the tagraxofusp dose may be continued during the next cycle at the same dose.

Otherwise tagraxofusp-related non-hematological toxicity not resolved to Grade ≤ 1 or baseline by day 28, the start of the next cycle will be delayed until resolution to Grade ≤ 1 or baseline up to a maximum of additional 28 (56 total) days.

After this treatment delay dosing may be continued during the next cycle at same dose.

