4.7 Discontinuation of treatment

Treatment will continue until maximal duration of maintenance therapy is reached (as specified in Section 4.0, Treatment Duration), or the occurrence of any of the following events:

- Disease progression
- Adverse event(s) that, in the judgment of the Investigator/Medical Monitor, may cause severe or permanent harm or which rule out continuation of maintenance study drug.
- Graft failure
- Development of grade III-IV acute GVHD
- Development of severe chronic GVHD
- Suspected pregnancy
- Inability to start planned cycle of tagraxofusp within 56 days of intended start date of each cycle.
- Major violation of the study protocol (to include subject noncompliance with study medications or protocol-specified procedures) at the discretion of the PI

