4.8 Procedures During Dosing Period

Monitor vital signs and check albumin, transaminases, and creatinine prior to preparing each dose of tagraxofusp. During each cycle, testing and procedures that may result in withholding of a scheduled tagraxofusp infusion, largely based on unresolved manifestations of fluid retention and/or other relevant acute toxicities during daily dosing, are described below. Details are presented in Table 3.

Table 3: Recommended Dose Modifications

Parameter	Severity Criteria	Dose Modification
Serum albumin	Serum albumin < 3.5 g/dL or reduced ≥ 0.5 g/dL from value measured prior to initiation of the current cycle	See CLS Management Guidelines (Appendix D.)
Body weight	Body weight increase ≥ 1.5 kg over pretreatment weight on prior treatment day	See CLS Management Guidelines (Appendix D.)
Aspartate aminotransferase (AST) or alanine aminotransferase (ALT)	ALT or AST increase > 5 times the upper limit of normal	Withhold tagraxofusp until transaminase elevations are ≤ 2.5 times the upper limit of normal.
Serum creatinine	Serum creatinine > 1.8 mg/dL (159 micromol/L) or creatinine clearance < 60 mL/minute	Withhold tagraxofusp until serum creatinine resolves to ≤ 1.8 mg/dL (159 micromol/L) or creatinine clearance ≥ 60 mL/minute.
Systolic blood pressure	Systolic blood pressure ≥ 160 mmHg or ≤ 80 mmHg	Withhold tagraxofusp until systolic blood pressure is < 160 mmHg or > 80 mmHg.
Heart rate	Heart rate ≥ 130 bpm or ≤ 40 bpm	Withhold tagraxofusp until heart rate is < 130 bpm or > 40 bpm.
Body temperature	Body temperature $\geq 38^\circ\text{C}$	Withhold tagraxofusp until body temperature is $< 38^\circ\text{C}$.

Parameter	Severity Criteria	Dose Modification
Hypersensitivity reactions	Mild or moderate	Withhold tagraxofusp until resolution of any mild or moderate hypersensitivity reaction. Resume tagraxofusp at the same infusion rate.
	Severe or life-threatening	Discontinue tagraxofusp permanently.

Except in conditions specified above, tagraxofusp may be re-administered subsequently in the same cycle, pending normalization of the abnormalities and pending evidence of stabilization of the underlying clinical conditions resulting in these abnormalities. Postponed doses may be administered within a 10-day period following the initial day of treatment within a cycle.

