8.0 Statistical Considerations

Type of study: Open label, single-arm, single center, Phase 2 clinical trial

Number of patients planned: 20

Expected accrual rate: 5-10 patients/year

Toxicity monitoring

Continuous monitoring of toxicity will be performed in all 20 patients. The first 3 patients will be treated with 9 mcg/kg in first 4 cycles. From cycle 5 and beyond in the first 3 patients, the dose will be 12 ug/kg/day. All subsequent patients will be treated with 12 ug/kg/day. Unacceptable toxicities are defined as tagraxofusp-related toxicities which prevent initiation of Cycle 2 of therapy (Any adverse event ³ grade 3 that is both a) considered related to tagraxofusp, and b) does not resolve to \leq grade 2 after a maximum delay of 56-days). Assuming a prior beta distribution of (0.4, 1.6), corresponding to an unacceptable toxicity rate of 30%, treatment will terminate if the $Pr(dt > 0.20 | \text{data}) > 0.95$, where dt is the toxicity rate attributable to the tagraxofusp treatment. The decision rule for terminating for toxicity is presented in Table 4 and the software used for this Bayesian toxicity monitoring rule is Multc Lean version 2.1.0. The operating characteristics for this rule are presented in Table 5. The method used to produce the decision rule and operating characteristics was designed by Thall, Simon, and Estey ^{26, 27} and extended by Thall and Sung. ²⁸

Table 4 Stopping criteria

Total Patients Enrolled	Stopping Condition (# of patients experiencing unacceptable toxicities)
3-4	3-4
5-8	4-8
9-11	5-11
12-14	6-14
15-18	7-18
19	8-19
20	Patient enrollment ends

Table 5 Operating characteristics

True % of DLTs	Pr (stopping early)	Average # of patients treated
0.05	0.00	20
0.10	0.01	20
0.20	0.11	19
0.30	0.38	16
0.40	0.70	12
0.50	0.91	9

Analysis

Demographic and baseline characteristics will be summarized. Categorical measures will be summarized using frequencies and percentages while continuous variables will be summarized using mean, standard deviation, median, minimum, and maximum.

The primary endpoint of the study is the tolerability of tagraxofusp post-SCT, where tolerability is defined as receipt of at least 75% of planned tagraxofusp doses in at least 4 cycles of therapy. The following table shows the exact 95% confidence intervals for different percentages of patients, out of 20 patients, experiencing tolerability:

Patients experiencing tolerability		95% Exact
Number	Percentage	Confidence Interval
2	10%	1.2% - 31.7%

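### Table 3's creatinine row releases a held dose on *or* where its trigger requires *and*, so neither renal limit can hold a dose on its own; correct the row and say how a stable pre-treatment clearance below 60 mL/min is handled.

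*Combined protocol and SAP*

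**What the plan says.** Table 3 in Section 4.8 gives the renal trigger as "Serum creatinine > 1.8 mg/dL (159 micromol/L) or creatinine clearance < 60 mL/minute" and the response as "Withhold tagraxofusp until serum creatinine resolves to ≤ 1.8 mg/dL (159 micromol/L) or creatinine clearance ≥ 60 mL/minute". The check is made before every dose, the first included: "Monitor vital signs and check albumin, transaminases, and creatinine prior to preparing each dose of tagraxofusp". The text below the table allows a held dose to be given later in the same cycle "pending normalization of the abnormalities and pending evidence of stabilization of the underlying clinical conditions resulting in these abnormalities", within 10 days of the cycle's first treatment day.

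The only renal entry limit is inclusion 8a: "Serum creatinine ≤ 1.5 mg/dL (133 mmol/L". Neither Section 3.1 nor Section 3.2 mentions CrCl, and no formula for it appears anywhere in the protocol.

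Two other rules bear on a prolonged hold. Section 4.7 ends treatment on "Inability to start planned cycle of tagraxofusp within 56 days of intended start date of each cycle". Section 8.0 sets the primary endpoint: "tolerability is defined as receipt of at least 75% of planned tagraxofusp doses in at least 4 cycles of therapy".

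**The concern.** The row states a safety limit and then cancels it. A hold for low CrCl is lifted by an acceptable creatinine, and a hold for high creatinine is lifted by an acceptable CrCl. Creatinine and CrCl are different measures that can disagree in the same patient, because CrCl also depends on age, weight and sex.

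The entry criteria make the disagreement likely to arise. Everyone who qualifies under 8a starts with creatinine at or below 1.5, and so already meets one release condition at 1.8. An older or lighter patient can nevertheless be below 60 mL/min. The table then calls for a hold and a release at the same check. It does not say whether a stable clearance that was below 60 before treatment is a reason to hold at all.

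What is at stake is mainly dosing safety: whether the CrCl limit does anything. Doses held or given also feed the tolerability endpoint, but that link is secondary and cannot be sized from the documents.

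**Working it through.** **Figure in the row.** 1.8 mg/dL × 88.42 = 159.2 micromol/L, which agrees with the 159 printed. (For 8a, 1.5 × 88.42 = 132.6 micromol/L, so the mmol/L there is a unit slip. It does not affect this point.)

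**Logic.** Let A be creatinine > 1.8 and B be CrCl < 60. The trigger is A or B. Its opposite is (not A) and (not B). The row releases on (not A) or (not B), which is the opposite of (A and B). A dose therefore stays held only when both limits are breached.

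| Creatinine (mg/dL) | CrCl (mL/min) | Trigger met | Release met as written | Release met with *and* |
|---|---|---|---|---|
| 1.4 | 70 | no | yes | yes |
| 1.4 | 50 | yes | yes | no |
| 2.0 | 70 | yes | yes | no |
| 2.0 | 50 | yes | no | no |

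Rows two and three are held and released at once. With *and*, no state is both.

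**Can an eligible patient be below 60?** Assumptions: Cockcroft-Gault, and weights of 70, 80 and 90 kg, since the documents give neither a formula nor weights.

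CrCl = (140 − age) × kg / (72 × creatinine), × 0.85 for women.

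Creatinine at which CrCl equals 60 = (140 − age) × kg / 4320, × 0.85 for women.

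Ages come from the background sections: 67 is the median in the 8-patient autologous series (Section 2.2.3), and 50 is the median in the US allogeneic series (Section 2.2.4).

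| Patient | 70 kg | 80 kg | 90 kg |
|---|---|---|---|
| Man, 67 | 73 × 70/4320 = 1.18 | 1.35 | 1.52 |
| Woman, 67 | 0.85 × 1.18 = 1.01 | 1.15 | 1.29 |
| Man, 50 | 90 × 70/4320 = 1.46 | 1.67 | 1.88 |

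Where the entry is below 1.5, creatinine values between it and 1.5 are eligible with CrCl below 60. That covers the 67-year-old man at 70 or 80 kg and the 67-year-old woman at all three weights. It leaves almost no room for the 50-year-old man.

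Example: a man aged 67, 76 kg, creatinine 1.4 has CrCl = 73 × 76/(72 × 1.4) = 55.0. He is eligible on 8a, meets the trigger before dose 1, and meets the release at the same moment.

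The other half of the fault also occurs, in heavier or younger patients. A man aged 50 at 90 kg with creatinine 1.85 has CrCl = 90 × 90/(72 × 1.85) = 60.8, so he too is held and released together.

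**Neighbouring rows.** Systolic pressure is released when it is below 160 or above 80, and heart rate when it is below 130 or above 40. Every possible value satisfies each of these.

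**The case against.** The best answer is that the intent is plain. The release mirrors the trigger, the literal reading would make the CrCl limit pointless, and the text below the table asks for normalization. The introduction to Table 3 says holds are largely for fluid retention or other acute toxicity during daily dosing, so a stable CrCl of 55 that predates the drug may not have been meant as a reason to hold. The table is headed as recommended, the trial has one center, and Section 5.4 requires that center's physician to approve dose or schedule changes. Exclusion 10 lets the investigator decline a patient at unacceptable risk.

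Much of this stands. It favours a stricter or an acute-change reading, and it rules out a claim of inconsistency between sites. It does not correct the stated rule. Nor does it choose between those two readings, which treat a stable baseline below 60 in opposite ways. Normalization cannot settle the matter for a patient whose usual value is below the limit.

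A reader might infer that such a patient is either dosed as usual or never dosed. That goes too far. The second outcome requires pairing each trigger with its own release, a CrCl that stays below 60, and an advisory table applied mechanically until the 56-day rule ends treatment.

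A reader might also infer a measurable shift in tolerability, since each patient is 1/20 = 5 points. The documents do not support that either. They give no count of patients below 60 at baseline, and any shift would depend on which patients form the denominator. The 14 of 125 (11.2%) in Table 2 are adverse-event reports of raised creatinine, not patients above 1.8, below 60 or held.

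**Conclusion.** The point holds as a fault in a stated safety rule. As written, neither renal limit works alone; only creatinine above 1.8 together with CrCl below 60 sustains a hold. This follows from the wording and needs no assumption.

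That eligible patients can be below 60 at the first dose rests on Cockcroft-Gault and the assumed weights. It applies mainly to older or lighter patients. How many of the 20 this would be is not in the documents. An effect on the tolerability endpoint is possible but unquantified. The correction is worth making because it is specific and nearly free, not because the primary result has been shown to depend on it.

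**What to change.** Creatinine row: withhold until *serum creatinine is ≤ 1.8 mg/dL and creatinine clearance (Cockcroft-Gault) is ≥ 60 mL/minute*.

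Add a rule for patients whose pre-treatment CrCl is below 60, because *and* alone would keep a stable patient held. Either hold and release on serum creatinine only (> 1.8 / ≤ 1.8 mg/dL), or use a stated change from baseline with a tolerance. This extends a principle already in Section 4.4, where after related non-hematological toxicity "the start of the next cycle will be delayed until resolution to Grade ≤ 1 or baseline". The tolerance matters: if the example patient's creatinine moves from 1.4 to 1.5, CrCl becomes 73 × 76/(72 × 1.5) = 51.4, and a bare return-to-baseline rule would hold him for a change of 0.1 mg/dL. Its size is a clinical choice for the sponsor.

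In the same edit, change *or* to *and* in the blood pressure and heart rate releases.

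Cost: a wording change and one value calculated from creatinine and weight already collected before infusion; no added visits or blood draws. A CrCl entry limit is optional and not part of this fix. It would exclude some older patients from a trial expecting 5-10 a year.

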4.9 Management of Specific Toxicities Capillary leak syndrome (CLS)

Capillary leak syndrome (CLS) is associated with vascular endothelial injury related to tagraxofusp administration and often occurs 3-8 days after initiation of treatment.

See Appendix D. for management of CLS and associated symptoms (hypoalbuminemia, edema, weight gain and hypotension).

In the setting of delays secondary to findings consistent with CLS (i.e., in the setting of resolved hypotension, tachycardia, increased weight, or albumin reductions of a magnitude lower than those warranting withholding of tagraxofusp for the duration of a given cycle), subsequent tagraxofusp is to be administered on days subsequent to the identification of the abnormality (not the same day), pending determination by the investigator that there is no/minimal evidence of ongoing CLS and pending discussion with the PI.

5.0 Evaluation During Study

Every effort will be made to adhere to the schedule of events and all protocol requirements. Variations in schedule of events and other protocol requirements that do not affect the rights and safety of the patient will not be considered as deviations. Such variations may include laboratory assessments completed outside of schedule and occasional missed required research samples. Missed samples for correlative studies will not constitute protocol deviations.

Table of Evaluations

	Pre-treatment ²	Pre-Infusion	Cycles 1-6 ¹					Cycles 7-12			Cycles 13+	
			Day 1	Day 2	Day 3	Day 7	Day 15 ⁵	Day 1	Day 2	Day 15 ⁵	Day 1	Day 2
Physical exam	X ³		X ⁴			X	X	X ⁴			X ⁴	
Vital signs	X	X	X	X	X	X	X	X	X	X	X	X
Weight	X	X	X	X	X	X	X	X	X	X	X	X
Lab tests	X ⁶	X ⁷	X	X	X	X	X		X	X	X	X
Pregnancy test	X ⁸											
12-lead EKG	X	X ⁹	X									
ECHO, PFTs	X											
Bone Marrow aspiration/biopsy	X ¹⁰											
CT (chest, abdomen, pelvis)	X											
Lumbar puncture	X ¹¹											
AE, SAE Monitoring		X	X	X	X	X	X	X	X	X	X	X

1 Cycle 1: Administered as inpatient. While in the hospital, the observation post-dosing should continue, as clinically indicated, until it is clear that the patient doesn't have evidence/symptoms of capillary leak syndrome (e.g., no weight gain, edema, hypotension, or decrease in albumin) or hypersensitivity reaction. At discharge after Cycle 1: At least once/week for 2 weeks: Physical exam, vital signs, weight, AE and SAE monitoring, clinical lab tests: CBC w/diff; serum electrolytes and chemistry (including albumin), and coagulation parameters.

2 Pre-treatment evaluations: Within 30 days of enrollment unless otherwise specified.

3 Physical exam, pre-treatment: Include detailed skin examination (+/- skin biopsy, as clinically indicated).

4 Physical exam, Cycles 1-6, Cycles 7-12 and Cycle 13+ Day 1: Within 48 hours of tagraxofusinfusion.

5 Day 15: (+/-3 days).

6 Pre-treatment labs: CBC with differential, serum chemistries including electrolytes, renal function tests, coagulation parameters, albumin, and liver function tests, lactate dehydrogenase (LDH), uric acid HIV/Hepatitis B and/or C.

7 Pre-infusion labs: CBC with differential, serum electrolytes and chemistry (including albumin), renal function tests, and liver function tests, lactate dehydrogenase (LDH), uric acid and coagulation parameters.

8 Serum or urine pregnancy test for women of child bearing potential (WOCBP), within 14 days of starting treatment.

9 12-lead EKG: Before infusion, Cycle 1 only.

10 Bone marrow aspiration and biopsy for pathologic review, immunophenotyping/flowcytometry, cytogenetic, molecular, and FISH analysis

11 Lumbar puncture for CSF analysis with routine CSF studies, cytology, and flow cytometry (optional, if not done previously and has history of CNS involvement).

5.1 Disease specific monitoring

Disease specific monitoring will be performed per Stem Cell Transplantation and Cellular Therapy guidelines.

5.2 Evaluations during follow up

All patients who do not discontinue study drug for toxicity will need to be followed for 30 days post-discontinuation to address any late developing toxicities which may occur. This follow up will cease when patients start a new therapy if prior to the 30-day follow up interval.

5.3 Duration of follow up

Participants will be followed for one year after removal from protocol therapy with either clinic visit or a phone call, or until death, whichever occurs first. Participants removed from protocol therapy for unacceptable adverse event(s) will be followed until resolution or stabilization of the adverse event.

5.4 Outside Physician Participation During Treatment

Starting Cycle 2, post tagraxofusp infusion: Laboratory tests and follow up visit can be performed locally and results sent to MDACC.

- 5.4.1 MDACC Physician communication with the outside physician is required prior to the patient returning to the local physician. This will be documented in the patient record.
- 5.4.2 A letter to the local physician outlining the patient's participation in a clinical trial will request local physician agreement to supervise the patient's care (Appendix E.).
- 5.4.3 Protocol required evaluations outside MDACC will be documented by telephone, fax or e-mail. Fax and/or e-mail will be dated and signed by the MDACC physician, indicating that they have reviewed it.
- 5.4.4 Changes in drug dose and/or schedule must be discussed with and approved by the MDACC physician investigator, or their representative prior to initiation, and will be documented in the patient record.
- 5.4.5 A copy of the informed consent, protocol abstract, treatment schema and evaluation during treatment will be provided to the local physician
- 5.4.6 Documentation to be provided by the local physician will include drug administration records, progress notes, reports of protocol required laboratory and diagnostic studies and documentation of any hospitalizations.
- 5.4.7 The home physician will be requested to report to the MDACC physician investigator all life threatening events within 24 hours of documented occurrence.
- 5.4.8 Patients will return to MDACC for each 28-day tagraxofusp infusion cycle.

6.0 Adverse Events and Reporting Requirements

An adverse event (AE) is the appearance or worsening of any undesirable sign, symptom, or medical condition occurring after starting the study drug even if the event is not considered to be related to study drug. Medical conditions/diseases present before starting study drug are only considered adverse events if they worsen after starting study drug. Abnormal laboratory values or test results constitute adverse events only if they induce clinical signs or symptoms, are considered clinically significant, or require therapy.

The investigator (or physician designee) is responsible for verifying and providing source documentation for all adverse events and assigning the attribution for all adverse events for subjects enrolled.

For the purpose of this study, the investigational component of the treatment plan is tagraxofusp (SL-401). Therefore, serious and unexpected adverse events occurring from the time of infusion of tagraxofusp up to 30 days of the last infusion of tagraxofusp, as defined below, will be reported according to MDACC policy and procedures below. The end of active treatment is the completion of the last infusion of tagraxofusp. Serious adverse events must be followed until clinical recovery and laboratory test have returned to baseline, progression of the event has stabilized, or there has been acceptable resolution of the event.

AEs will graded according to the NCI Common Terminology Criteria for Adverse Events (CTCAE) version 5.0. A copy of CTCAE version 5.0 can be downloaded from the CTEP website https://ctep.cancer.gov/protocolDevelopment/electronic_applications/ctc.htm#ctc_50

Grade – Severity of the adverse event. Grades were developed using the following guidelines:

- Grade 0 – No adverse event or within normal limits
- 1 – Mild adverse event
- 2 – Moderate adverse event
- 3 – Severe adverse event
- 4 – Life-threatening or disabling adverse event
- 5 – Fatal adverse event

Abnormal laboratory values not included in the CTCAE guidelines will be defined per protocol.

Time for AE Collection

Adverse events will be collected from the start of the study drug until 30 days after the last infusion of tagraxofusp.

Adverse Event Reporting

The Investigator or physician designee is responsible for verifying and providing source documentation for all adverse events, and assigning attribution for each event on all subjects enrolled on this study.

Data collection

Collection of adverse events will reflect the onset and resolution date and maximum grade. Intermittent events should be labeled as such and followed until resolution. If a patient is taken off study while an event still ongoing, this will be followed until resolution unless another therapy is initiated. Pre-existing medical conditions will be recorded only if an exacerbation occurs during the active treatment period.

Patients will be registered in MD Anderson's Clinical Trial Management System, OnCore.

Adverse events and all protocol specific data will be entered into the electronic case report form (REDCap).

Events not to be considered adverse events in this study are those related to original disease or expected in the post-allogeneic transplant period.

Isolated changes in laboratory parameters such as electrolyte, magnesium and metabolic imbalances, uric acid changes, elevations of LDH and alkaline phosphatase will not be monitored.

Concomitant medications

Patients treated on this protocol will require supportive care treatment (concomitant medications). These medications are considered standard of care and have no scientific contribution to the protocol; therefore no data will be captured on various medications needed or their side effects. All antiviral therapy will be captured in the medical record.

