- OnCore, will be utilized for safety reporting to the IND Office and MDACC IRB.
- Serious adverse events will be captured from the time of the first protocol-specific intervention, until 30 days after the last dose of drug, unless the participant withdraws consent. Serious adverse events must be followed until clinical recovery is complete and laboratory tests have returned to baseline, progression of the event has stabilized, or there has been acceptable resolution of the event.
- Additionally, any serious adverse events that occur after the 30 day time period that are related to the study treatment must be reported to the IND Office. This may include the development of a secondary malignancy.

Reporting to FDA:

- Serious adverse events will be forwarded to FDA by the IND Sponsor (Safety Project Manager IND Office) according to 21 CFR 312.32. A copy of this form will be submitted to Stemline Therapeutics at the same time it is submitted to the IND Office.

It is the responsibility of the PI and the research team to ensure serious adverse events are reported according to the Code of Federal Regulations, Good Clinical Practices, the protocol guidelines, the sponsor's guidelines, and Institutional Review Board policy.

Recommended Adverse Event Recording Guidelines

Attribution	Grade 1	Grade 2	Grade 3	Grade 4	Grade 5
Unrelated	Phase I	Phase I	Phase I	Phase I	Phase I
			Phase II	Phase II	Phase II
				Phase III	Phase III
Unlikely	Phase I	Phase I	Phase I	Phase I	Phase I
			Phase II	Phase II	Phase II
				Phase III	Phase III
Possible	Phase I	Phase I	Phase I	Phase I	Phase I
	Phase II	Phase II	Phase II	Phase II	Phase II
		Phase III	Phase III	Phase III	Phase III
Probable	Phase I	Phase I	Phase I	Phase I	Phase I
	Phase II	Phase II	Phase II	Phase II	Phase II
		Phase III	Phase III	Phase III	Phase III
Definitive	Phase I	Phase I	Phase I	Phase I	Phase I
	Phase II	Phase II	Phase II	Phase II	Phase II
		Phase III	Phase III	Phase III	Phase III

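### Section 6.0 gives two conflicting windows for recording worsening of a pre-existing condition, so non-serious worsening in the 30 days after the last dose may go unrecorded

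*Combined protocol and SAP*

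**What the plan says.** All but two of the relevant statements are in Section 6.0 of the combined protocol and SAP.

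- Definition of an adverse event: "Medical conditions/diseases present before starting study drug are only considered adverse events if they worsen after starting study drug". Worsening at any time after the first dose therefore qualifies.
- Time for AE Collection: "Adverse events will be collected from the start of the study drug until 30 days after the last infusion of tagraxofusp".
- Data collection: "Pre-existing medical conditions will be recorded only if an exacerbation occurs during the active treatment period".
- Meaning of active treatment: "The end of active treatment is the completion of the last infusion of tagraxofusp".

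Section 6.1 has its own rule for serious events: "Serious adverse events will be captured from the time of the first protocol-specific intervention, until 30 days after the last dose of drug". It adds a rule for later events, with the IND Office as recipient: "any serious adverse events that occur after the 30 day time period that are related to the study treatment must be reported to the IND". Neither sentence makes an exception for pre-existing conditions.

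Section 5.2 states why patients are observed after the last dose. Those who do not stop for toxicity are "followed for 30 days post-discontinuation to address any late developing toxicities which may occur", unless new therapy begins sooner.

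**The concern.** For the 30 days after the last infusion, Section 6.0 gives two instructions that cannot both be followed. The definition and the collection window say that worsening of an existing condition is recorded. The data-collection paragraph says that it is not. That paragraph is the more specific instruction and carries the word *only*, so a data manager could reasonably follow it.

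Three features make this more than a drafting matter.

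- The primary objective (Section 1.0) is safety. The Phase II entries of the recording table in Section 6.1 call for possibly, probably and definitely related events of every grade, so non-serious events are meant to be in the data.
- Patients may enter with abnormal baselines. Section 3.1 admits albumin down to 3.2 g/dL, transaminases up to 2.5 times the upper limit of normal, hemoglobin from 8 g/dL and platelets from 50,000. Some drug effects may therefore appear as worsening of something already present.
- Drug effects can appear after the dosing days. Section 4.4 gives infusions on Days 1 to 3 (Cycles 1-4) or Days 1 and 2 (Cycle 5 onward), while Section 4.9 says that capillary leak syndrome "often occurs 3-8 days after initiation of treatment".

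**Working it through.** The plan states no figure on this point, so there is none to reproduce. The check compares the windows and then measures the disputed period.

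**Step 1: windows side by side**

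| Event | Governing text | Recording ends |
|---|---|---|
| New adverse event | 6.0, Time for AE Collection | 30 days after last infusion |
| Worsening of a pre-existing condition, by definition and general window | 6.0, definition and Time for AE Collection | 30 days after last infusion |
| Worsening of a pre-existing condition, by recording rule | 6.0, Data collection, with the stated end of active treatment | Last infusion |
| Any serious event | 6.1 | 30 days after last dose; later if related |

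Rows two and three conflict. Row four limits the exposure to non-serious worsening.

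**Step 2: the narrow rule makes recording depend on later treatment**

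Take a non-serious worsening on Day 8 of Cycle 1, with infusions on Days 1-3. I assume that active treatment runs without a break from the first infusion to the last, since the protocol states only where it ends.

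- If Cycle 2 is given on schedule, its first infusion is on Day 29. Day 8 precedes the last infusion and is recorded.
- If no further dose is given, the last infusion was on Day 3. Day 8 falls 5 days after it and is not recorded.

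The event is the same in both cases. What differs is whether the patient goes on, which the event itself may influence.

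**Step 3: share of the adverse event window in dispute**

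Inputs: 28-day cycles, with the last infusion on Day 3 of the cycle (Cycles 1-4) or Day 2 (Cycle 5 onward), from Section 4.4; 30 days of collection afterwards, from Section 6.0. No delays are assumed.

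Last infusion day D = 28 × (c − 1) + k, where c is the number of cycles and k is 3 or 2. The window is D + 30 days, and the disputed share is 30 / (D + 30).

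| Cycles received | D | Window (days) | Disputed share |
|---|---|---|---|
| 1 | 3 | 33 | 30/33 = 91% |
| 4 | 28 × 3 + 3 = 87 | 117 | 30/117 = 26% |
| 12 | 28 × 11 + 2 = 310 | 340 | 30/340 = 9% |
| 24 | 28 × 23 + 2 = 646 | 676 | 30/676 = 4% |

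Section 4.8 lets postponed doses be given within 10 days of a cycle's first treatment day. If the last Cycle 1 infusion moves to Day 10 or 11, the one-cycle share becomes 30/40 = 75% or 30/41 = 73%.

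These are shares of calendar time. In absolute terms the disputed period is the same 30 days for everyone; only its proportion is larger in early stoppers. The documents give neither a rate of such worsening nor an expected number of one-cycle stoppers, so events lost cannot be computed.

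**The case against.** The strongest reply is that the documents show ambiguity and not loss. Section 6.0 itself calls later worsening an adverse event and collects events for 30 days. Other provisions keep the patient under observation: adverse event monitoring on Days 7 and 15 of Cycles 1-6 and at least weekly for two weeks after Cycle 1 discharge (Section 5.0), post-dose observation for capillary leak (4.5), 30-day follow-up (5.2), and follow-up of unacceptable events to resolution or stabilization (5.3). Section 6.1 also lets important medical events be reported as serious without hospitalization.

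Part of this stands. Loss is a risk that depends on which sentence a site follows. But the observation provisions determine what is seen; they do not override a data-collection rule about what is recorded.

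The scope is also limited, and these limits stand:

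- New capillary leak syndrome is a new event and is collected for 30 days in any case. Its timing shows only that drug effects can follow the dosing days.
- Section 3.2 excludes persistent clinically significant non-hematologic toxicity of grade 2 or more, with few exceptions, which narrows the pool of baseline conditions.
- Other sentences in Section 6.0 set aside events related to the original disease or expected after allogeneic transplant, certain isolated laboratory changes, and laboratory abnormalities without clinical consequence. Some worsening of chronic GVHD or of cytopenias may be excluded on those grounds, whatever the window.

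A reader might infer that the stopping rule in Section 8.0 will undercount. The documents do not establish this. That rule counts related events of grade 3 or more that prevent Cycle 2, judged over a delay of up to 56 days, so it already requires assessment after the last infusion. A non-serious worsening of a baseline condition could still be caught by the recording conflict, but nothing in the documents sizes that possibility.

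**Conclusion.** The point holds as an internal inconsistency. Section 6.0 sets two end points, 30 days apart, for recording worsening of a pre-existing condition. If the narrower rule is followed, non-serious worsening after the last dose may go unrecorded, and recording of a given event then turns on whether the patient is dosed again. Any loss is confined to the period after the final infusion and is proportionally largest in early stoppers.

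This rests on reading *active treatment period* in the data-collection paragraph by the end point that the same section gives for active treatment. The shares of the window assume the Section 4.4 schedule without delays.

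Three stronger readings are tempting and unsupported. Such worsening does not necessarily drop out of the safety data, because the definition and general window in Section 6.0 point the other way. The 91% does not describe patients in general or events lost; it is the time share for a patient who stops after one cycle with no delay. The primary tolerability endpoint is not directly affected, because Section 8.0 defines it by doses received.

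The change is worth making because the trial's primary objective is safety and the correction is small.

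**What to change.** In the data-collection paragraph of Section 6.0, replace the reference to active treatment with the general window, so that exacerbations of pre-existing conditions are recorded *from the first infusion until 30 days after the last infusion of tagraxofusp*. Make the same change in any case report form completion instructions that repeat the rule.

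The cost is one protocol sentence and a few more adverse event entries per patient. No added visits, patients or analyses are needed. The separate exclusions for disease-related events, events expected after transplant and isolated laboratory changes remain as they are, so the edit will not bring those into the data.
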